12.2 Record Retention

The investigator agrees to keep the records stipulated in [Appendix A](#) and those documents that include (but are not limited to) the trial-specific documents, the identification log of all participating subjects, medical records, temporary media (e.g., thermal sensitive paper, and should be copied and certified), source worksheets, all original signed and dated ICFs, subject authorization forms regarding the use of personal health information (if separate from the ICFs), eCRFs, including the audit trail, and detailed records of vaccine disposition to enable evaluations or audits from regulatory authorities, the sponsor or designee.

Furthermore, ICH E6 Section 4.9.5 requires the investigator to retain essential documents specified in ICH E6 (Section 8) until at least 2 years after the last approval of a marketing application for a specified vaccine indication being investigated or, if an application is not approved, until at least 2 years after the investigation is discontinued and regulatory authorities are notified. In addition,

ICH E6 Section 4.9.5 states that the trial records should be retained until an amount of time specified by applicable regulatory requirements or for a time specified in the clinical trial site agreement between the investigator and sponsor.

Refer to the clinical trial site agreement for the L requirements on record retention. The investigator should contact and receive written approval from the sponsor before disposing of any such documents.

13.0 STATISTICAL METHODS

13.1 Statistical and Analytical Plans

A statistical analysis plan will be prepared and finalized prior to unblinding of the trial groups. This document will provide further details regarding the definition of analysis variables and analysis methodology to address all trial objectives.

A (blinded) data review will be conducted prior to unblinding of the trial groups. This review will assess the accuracy and completeness of the trial database, subject evaluability, and appropriateness of the planned statistical methods.

13.1.1 Analysis Sets

Safety Set: The safety set will consist of all subjects who received a dose of IVX-A12 or placebo. Subjects will be analyzed as treated.

Full Analysis Set (FAS): The FAS will include all randomized subjects who received a dose of IVX-A12 or placebo. Subjects will be analyzed as randomized.

Per-Protocol Set (PPS): The PPS will include all subjects in the FAS who received a dose of IVX-A12 or placebo and have no major protocol deviations that have a significant impact on immunogenicity results. Subjects will be analyzed as randomized.

Extension Enrolled Set: The Extension Enrolled Set will consist of all subjects who consented to participate in the extension portion of the trial. Subjects will be analyzed as initially treated.

13.1.2 Analysis of Disposition, Demographics, Other Baseline Characteristics, Medical History and Medications

Subject disposition will be summarized for all enrolled subjects which will include the number of subjects enrolled, screen failed, and randomized. For subjects who are randomized, the number and percentage of subjects in each of the analysis sets will be summarized by treatment group.

Demographics (age, gender, race) and other baseline characteristics (including baseline RSV and hMPV NAb titers) will be summarized descriptively by treatment group for all randomized subjects.

Medical and surgical history will be summarized by primary SOC and PT and by vaccine group. All medical history data will be listed.

All prior and concomitant medications will be summarized by Anatomical Therapeutic Chemical Level 4 and PT and by treatment group. All medications will be listed.

13.1.3 Immunogenicity Analyses

Immunogenicity data will be summarized for each group and strain (RSV/A, RSV/B, both RSV strains and either RSV strain; hMPV/A, hMPV/B, both hMPV strains and either hMPV strain). The GMT will be calculated for RSV/A, RSV/B, hMPV/A and hMPV/B titers separately along with their 95% CI. The adjusted GMT and corresponding 95% CI will be obtained from an analysis of covariance (ANCOVA) model, which will include log-transformed baseline titers, age group, and treatment group as terms. Durability will be assessed at Days 180, 365, and at Day 730 by comparing to Day 28 data. The geometric mean of fold changes and corresponding 95% CI will be calculated.

Proportion of subjects with h-fold increase (SRR), 8-fold increase, and GMFR from prevaccination/baseline (Day 0) will be summarized for Days 28, 180, 365, and at Day 730. RCD curves will be generated.

The VLP core-specific IgG titers will be summarized at Days 0, 28, 180, 365, and Day 730 with GMT and 95% CI.

Separate summaries will be provided for subjects that agreed to participate in the Y q ° ^ L°*q qL ^ Lv ^ Lv Brćqv °*pL..v **vLN* ..qvćq qv YćqN v..° °v from the beginning of the trial through Day 730.

All immunogenicity data will be listed.

13.1.4 Efficacy Analysis

RSV and/or hMPV cases of mild, moderate, or severe LRTI and any severity LRTI due to RSV and/or hMPV (CESIs), meeting the protocol-specified definitions, will be summarized by vaccine group and placebo group starting on Day 14 through Day 365. Listings will be provided.

Vaccine efficacy will be calculated as $100 \times (1 - \text{incidence rate ratio})$. The incidence rate is the number of subjects meeting the case definition divided by cumulative follow-up person time among all subjects at risk. The incidence rate ratio is the ratio between the incidence rates of vaccine group and placebo group.

13.1.5 Safety Analyses

Solicited local (injection site) reactions and solicited systemic ARs: Solicited ARs will be summarized for 7 days starting from the day of dosing (Day 0) through Day 6 (total of 7 days). The summary will be by day and overall, within 7 days. Solicited ARs by maximum severity will also be summarized.

Unsolicited AEs: Unsolicited AEs will be assessed from day of dosing (Day 0) through 28 days post-vaccination and coded according to MedDRA and summarized by SOC and PT. The summary tables will include the number and percentage of

subjects reporting unsolicited AE by SOC and PT, and by SOC, PT, and maximum severity. Subjects reporting 5 °..q 3 and vaccine-related unsolicited AEs will also be summarized.

SAEs, MAAEs, AESIs, AEs leading to withdrawal, and CESI (mild, moderate, or severe LRTI caused by RSV and/or hMPV) and mild, moderate, or severe LRTI cases not caused by RSV or hMPV will be assessed throughout the trial (from randomization on Day 0) and coded using MedDRA and summarized by SOC and PT. For the trial extension, SAEs, MAAEs, and AESIs will be continue to be collected and coded. Separate summaries will be provided for subjects that agreed to participate in the extension port` Lv B/ćqv `*vL...v **vLN* ..qvćq qv YćqN v..o °v from the beginning of the trial through Day 730.

All solicited ARs and unsolicited AEs will be listed.

Clinical laboratory tests including hematology, chemistry, and urinalysis will be summarized by vaccine groups. For numeric laboratory parameters, the observed value and change from baseline will be summarized by visit. For categorical laboratory parameters, the number of subjects and percentages will be summarized by visit. Shift tables may be provided as well. All lab data will be listed.

All vital signs observed value and change from baseline will be summarized by vaccine groups. Listing will also be provided.

Physical examination results will be listed.

13.2 Interim Analysis/Data Reviews

Two IAs will be performed: The first IA will be performed after all subjects have completed the Day 28 safety assessments and when all Day 28 immunogenicity data are available; the second IA will be performed after all subjects have completed the Day 180 safety assessments, and when all Day 180 secondary immunogenicity data are available. A final analysis of main trial will be performed after Day 365 and an analysis of the observational extension will be performed after Day 730. These analyses will support further evaluation of safety and immunogenicity of IVX-A12 in older adults.

13.3 Primary and Secondary Analyses for the CSR

A CSR will be prepared when Day 365 analyses have been completed for the primary and secondary objectives of the trial. Additional analyses including safety and immunogenicity through Day 730 may be provided in a Clinical Study Addendum.

13.4 Sample Size Justification

Sample size for this trial is not based on any formal hypothesis testing. Analyses of safety and immunogenicity will be primarily descriptive in nature. An approximate total of 250 subjects (approximately 100 subjects in each of the IVX-A12 groups and 50 subjects in the placebo group) will be randomized. With 100 subjects in each IVX-A12 group, there is a 63.4% probability of observing at least 1 subject with an AE if the true incidence of the AE is 1%, and 86.7% probability of observing at least 1 subject with an AE if the true incidence of the AE is 2%. The trial will have more than 90% power to detect a difference of 20% or more in SRR or detect a 2-fold increase or more in GMT or GMFR (assuming standard deviation at $0.5 \log_{10}$), between the two IVX-A12 groups (or between the IVX-A12 group and placebo group), with two-sided type-1 error rate at 0.05.

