4.3. Determination of Sample Size

4.3.1. Main Trial Determination of Sample Size

Sample size for this trial is not based on any formal hypothesis testing. Analyses of safety and immunogenicity will be primarily descriptive in nature. An approximate total of 250 subjects (approximately 100 subjects in each of the IVX-A12 groups and 50 subjects in the placebo group) will be randomized. With 100 subjects in each IVX-A12, there is a 63.4% probability of observing at least 1 subject with an AE if the true incidence of the AE is 1% and 86.7% probability of observing at least 1 subject with an AE if the true incidence of the AE is 2%. The trial will have more than 90% power to detect a difference of 20% or more in seroresponse rate (SRR) or detect a 2-fold increase or more in GMT or GMFR (assuming standard deviation at $0.5 \log_{10}$), between the two IVX-A12 groups (or between the IVX-A12 group and placebo group), with a two-sided type-1 error rate at 0.05.

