7.1. General Methods

- No formal statistical hypotheses to be tested for the study. 95% confidence interval (CI) and p-value are presented for data nature.
- Unless otherwise specified, summaries will be presented by vaccine group, aggregate IVX-A12, and overall.
- Vaccine groups will be categorized as:
 - Main Trial:
 - 150 µg RSV/ 150 µg hMPV IVX-A12a (unadjuvanted)
 - 150 µg RSV/ 150 µg hMPV IVX-A12d (adjuvanted with MF59®)
 - Placebo
 - Observational Extension Trial:
 - 150 µg RSV/ 150 µg hMPV IVX-A12a (unadjuvanted)
 - Placebo

Aggregate IVX-A12 includes 150 µg RSV/ 150 µg hMPV IVX-A12a (unadjuvanted) and 150 µg RSV/ 150 µg hMPV IVX-A12d (adjuvanted with MF59®).

- All listings will display age, sex, and race.
- Continuous variables will be summarized using the number of observations (n), mean, standard deviation (SD), median, minimum, and maximum. Additionally, quartiles will be provided for continuous variables related to immunogenicity. The same number of decimal places as in the raw data will be presented when reporting minimum and maximum; 1 more decimal place than in the raw data will be presented when reporting mean, median, least squares, and quartiles; and 2 more decimal places than in the raw data will be presented when reporting SD. No more than 3 decimal places will be presented. For confidence intervals (CIs) for mean will be presented with the same decimal places as the mean. For p-values and correlations, 3 decimal places will be presented. P-values <0.001 and >0.999 will be presented as '<0.001' and '>0.999', respectively.
- Descriptive statistics for categorical/qualitative data will include frequency counts and percentages. The total number of subjects in each vaccine group and placebo will be used as the denominator for percentage calculations, unless stated otherwise in the table shell. All percentages will be presented with one decimal point, unless specified otherwise. For percentages equal to 100 will show as 100 rather than 100.0.

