9.1. Main Trial Immunogenicity

The immunogenicity analyses will be performed on the PPS, unless otherwise stated. Immunogenicity results will be excluded if the study day collected occurs outside of the analysis windows as indicated in [Table 3](#).

All data will be listed, for the FAS, until the end of the main trial.

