Using an ANCOVA, the adjusted GMTs and GMFRs at Day 28 and its 95% CI will be calculated. The outcome variable is Day 28 log2 transformed titers. The factors will include vaccine group, age stratification category, and gender and the covariates will include, log2 transformed baseline titers. Least square means and 95% CIs are back transformed to provide geometric means. To assess whether an adjuvant is required in the formulation to enhance immune responses to IVX-A12, pairwise comparison of the GMT and GMFR least square means from this modeling between non-adjuvant and adjuvant groups will also be displayed. Also, to assess an improvement between the active treatments (IVX-A12a and IVX-A12d) versus placebo, pairwise comparison of the GMT and GMFR least square means from this modeling between IVX-A12a and Placebo and IVX-A12d and Placebo will be displayed. No adjustments for multiplicity will be performed. Data displays will also include boxplots of titers for anti-RSV/A-, RSV/B-, hMPV/A-, and hMPV/B specific NAb ([live-virus assays]) and RSV and hMPV IgG prefusion F protein-specific antibody titers ([ELISAs] at Day 28 for all ages. Log2 transformed titers will be used to create boxplots and back-transformed. The y-axis will be on a log scale. For anti-RSV/A- and RSV/B, the y-axis will display both sets of units.

The above analysis will be repeated as follows:

- By age subgroup analyses category. When using an ANCOVA, the outcome variable is Day 28 log2 transformed titers. The factors will include vaccine group, age stratification category and gender and the covariate is log2 transformed baseline titers;

This document is confidential.

- By baseline tertile; When using an ANOVA, the outcome variable is Day 28 log2 transformed titers. The factors will include vaccine group, age stratification category and gender;
- By age subgroup analyses category and baseline tertile. When using the ANOVA, the factors will include vaccine group, age stratification category, and gender.

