9.1.1.2. Analysis of Subjects with a ≥ 4 -Fold Increase

The proportion of subjects with a ≥ 4 -fold increase in serum anti-RSV/A-, RSV/B-, hMPV/A-, hMPV/B-specific NAb (live-virus assays), RSV and hMPV IgG prefusion F protein-specific antibody titers will be calculated at Day 28 and summarized by vaccine group for each of the following: RSV-A, RSV-B, both RSV strains, either RSV strains, hMPV-A, hMPV-B, both hMPV strains, either hMPV strains, RSV and hMPV IgG prefusion F protein-specific antibody titers. The 95% CI of the difference in proportion of subjects with a ≥ 4 -fold increase in serum anti-RSV/A-, RSV/B-, hMPV/A-, hMPV/B-specific NAb (live-virus assays), RSV and hMPV IgG prefusion F protein-specific antibody titers between vaccine groups with and without adjuvant and IVX-A12a versus Placebo and IVX-A12d versus Placebo will be computed using Wilson's score method. Logistic regression models will be used to further describe the IVX-A12d response to vaccination when compared to IVX-A12a. Also, logistic regression models will be used to describe the response of IVX-A12a versus Placebo and the response of IVX-A12d versus Placebo. The outcome variable is binary (≥ 4 -fold increase or no ≥ 4 -fold increase). Vaccine group, log2 transformed baseline NAb titer, age stratification category, and gender are included as explanatory variables.

The ≥ 4 -fold increase analyses will be repeated for the following:

- By vaccine group and age subgroup analyses category. For the logistic regression models, vaccine group, log2 transformed baseline titer, age stratification category and gender are included as the explanatory variables;
- By vaccine group and baseline tertile; For the logistic regression models, vaccine group, age stratification category and gender are included as the explanatory variables;
- By vaccine group and age subgroup analyses and baseline tertile. For the logistic regression models, vaccine group, age stratification category and gender are included as the explanatory variables.

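### The stated power of more than 90% for a 20-point SRR difference names no SRRs and fails at mid-range rates: about 81% for 100 v 100 at 40% v 60%, and about 82% for 100 v 50 at 10% v 30%

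*Protocol*

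**What the plan says.** Protocol 13.4 states: "The trial will have more than 90% power to detect a difference of 20% or more in SRR", "with two-sided type-1 error rate at 0.05". The Sample Size Justification in Protocol 2.0 says the same, and SAP 4.3.1 repeats it: "more than 90% power to detect a difference of 20% or more in seroresponse rate (SRR". The claim is made for contrasts "between the two IVX-A12 groups (or between the IVX-A12 group and placebo group", that is 100 v 100 and 100 v 50.

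The same sentence gives a planning SD of 0.5 log10 for GMT and GMFR. It gives no corresponding input for SRR: no rate in any group, no test and no evaluable number.

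SRR at Day 28 (a rise of at least 4-fold from Day 0) is a co-primary immunogenicity endpoint in SAP 5.1.1.2. SAP 9.1.1.2 plans 95% intervals for the SRR difference "between vaccine groups with and without adjuvant and IVX-A12a versus Placebo and IVX-A12d versus Placebo will be computed using Wilson's score method". On the population, SAP 9.1 says: "The immunogenicity analyses will be performed on the PPS, unless otherwise stated". On the status of testing, SAP 7.1 says: "No formal statistical hypotheses to be tested for the study".

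**The concern.** The variance of a difference in proportions is largest when the rates are near 50% and shrinks towards 0% or 100%. A 20-point difference therefore has no single power at fixed group sizes. The plan nonetheless states one lower bound, without condition, for two contrasts of different size. The reader cannot verify it, and it may be false at the rates that occur.

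The interval for IVX-A12a against IVX-A12d is where this matters most, since mid-range rates are possible in both groups. If that interval includes zero, a reader who trusts the stated power would treat a true 20-point difference as having had less than a 10% chance of being missed. At 40% v 60% the chance is about 19%.

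**Working it through.** **Inputs from the documents.** Groups of 100, 100 and 50; two-sided alpha 0.05; a difference of 20%, read as percentage points; SD 0.5 log10 for titres. The SRRs below are assumptions, scanned over the possible range.

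**The section's other figures reproduce.**
- Chance of at least one AE among 100 subjects: 1 − 0.99^100 = 63.4%; 1 − 0.98^100 = 86.7%.
- 2-fold GMT ratio, log10(2) = 0.301, normal approximation:
  - 100 v 100: SE = 0.5 × √(2/100) = 0.0707; power = Φ(0.301/0.0707 − 1.96) = Φ(2.30) = 98.9%.
  - 100 v 50: SE = 0.5 × √(1/100 + 1/50) = 0.0866; power = Φ(1.52) = 93.5% (93.2% with the t distribution).

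**SRR formula (pooled normal approximation).** With pooled rate p̄:
- SE0 = √[p̄(1 − p̄)(1/n1 + 1/n2)]
- SE1 = √[p1(1 − p1)/n1 + p2(1 − p2)/n2]
- power = Φ[(0.20 − 1.96 × SE0)/SE1]

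**100 v 100 at 40% v 60%.** p̄ = 0.50; SE0 = 0.0707; SE1 = 0.0693. Power = Φ[(0.20 − 0.1386)/0.0693] = Φ(0.886) = 81.2%.

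**100 v 50 at placebo 10% v active 30%.** p̄ = (5 + 30)/150 = 0.233; SE0 = √(0.1789 × 0.03) = 0.0733; SE1 = √(0.0018 + 0.0021) = 0.0625. Power = Φ[(0.20 − 0.1436)/0.0625] = Φ(0.903) = 81.7%.

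**Across rates**, with exact binomial enumeration as a check on the method. The Wilson column is the chance that a Newcombe-Wilson 95% interval for the difference excludes zero; SAP 9.1.1.2 names only Wilson's score method, so the Newcombe form is an assumption.

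| Contrast | Rates | Pooled normal | Wilson interval | Fisher |
|---|---|---|---|---|
| 100 v 100 | 10% v 30% | 94.8% | 95.3% | 93.5% |
| 100 v 100 | 20% v 40% | 87.6% | 88.0% | 84.4% |
| 100 v 100 | 30% v 50% | 82.8% | 83.2% | 79.2% |
| 100 v 100 | 40% v 60% | 81.2% | 82.6% | 78.7% |
| 100 v 50 | 2% v 22% | 95.5% | 96.9% | 97.0% |
| 100 v 50 | 5% v 25% | 90.2% | 91.2% | 90.9% |
| 100 v 50 | 8% v 28% | 84.9% | 85.6% | 84.9% |
| 100 v 50 | 10% v 30% | 81.7% | 82.4% | 81.4% |

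**Where power exceeds 90%.**
- 100 v 100: lower SRR at most 16.4% or at least 63.6% (Wilson interval 16.7% and 63.3%).
- 100 v 50: placebo SRR at most 5.1% or at least 73.6% (Wilson interval 5.6% and 72.6%).

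The lower rate can run from 0% to 80%. Power is therefore below 90% over (63.6 − 16.4)/80 = 59% of that range for 100 v 100, and (73.6 − 5.1)/80 = 86% for 100 v 50. The minima are about 81% and about 64%, both near 40% v 60%.

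**Difference that does have more than 90% power at every pair of rates (pooled normal).** About 23 points for 100 v 100 and about 28 points for 100 v 50.

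**Evaluable number.** The analysis uses the PPS, and SAP 7.5 excludes out-of-window samples. The documents give no loss rate. With an assumed 10% loss (90, 90 and 45 subjects), power is 77% for 40% v 60%, 77% for 10% v 30% against placebo, and 86% for 5% v 25% against placebo.

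**The case against.** The sponsor's own calculation has not been shown to be wrong. Its input rates are missing, and the 40% v 60% and 10% v 30% pairs are illustrations chosen for this check. Placebo is an aqueous diluent, so a 4-fold rise by Day 28 may well be rare. At placebo rates of 0% to 5% the claim holds at full size (98.3% to 90.2%). An unpooled variance is also kinder to the placebo contrast: 89.3% at 10% v 30%, with the 90% cut-off near 9.5%.

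The consequence is also small. The trial is declared descriptive. SAP 9.1.1.1 ties the adjuvant question to "pairwise comparison of the GMT and GMFR least square means from this modeling between non-adjuvant and adjuvant groups", whose stated power holds. Enrolment is complete, and the unadjuvanted formulation was chosen after the Day 28 interim analysis. The planned intervals will show the precision achieved at the observed rates.

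Most of this stands as a limit on importance. It does not rescue the sentence. A low placebo rate is nowhere stated as the planning assumption, and it would not help the comparison of the two IVX-A12 groups. No method tried reaches 90% there at 40% v 60%: unpooled gives 82.3%, and even a one-sided 0.05 test gives 88.6%. In the placebo contrast the Wilson interval, which is closest to the planned analysis, agrees with the pooled figure rather than the unpooled one. Descriptive status does not excuse a power figure that is published with its own alpha.

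**Conclusion.** The concern holds. As an unconditional statement, more than 90% power for a 20-point SRR difference is wrong for both contrasts. It is true only towards the ends of the rate range. Elsewhere power falls to about 81% for the two IVX-A12 groups and to about 64% against placebo. These figures assume full groups of 100, 100 and 50 and two-sided 0.05; PPS losses would lower them. Whether power fell short in this trial depends on rates the documents do not give. The effect is on how the co-primary SRR contrasts are read. No decision rule, design feature or planned analysis depends on it. It should be fixed because the figure appears in three places and the correction is simple.

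**What to change.** In Protocol 2.0, Protocol 13.4 and SAP 4.3.1, state the SRRs assumed for each contrast, the method and the evaluable numbers, and quote the power at those rates. If no planning rates existed, give the range instead, for example:

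> Assuming 100 evaluable subjects per IVX-A12 group and a two-sided 0.05 comparison of proportions (pooled normal approximation), power for a 20-point SRR difference between the IVX-A12 groups ranges from about 81% (40% v 60%) to over 90% (lower SRR at most 16% or at least 64%). Against 50 evaluable placebo subjects, power exceeds 90% if the placebo SRR is at most 5% or at least 74%, is about 82% at 10% v 30%, and has a minimum of about 64% near 40% v 60%.

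Leave the GMT/GMFR statement as it is. The cost is wording in three places, with no added subjects and no change to any analysis. The stated SRR power becomes conditional and, at mid-range rates, lower.
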